7.2 PRIMARY EFFECTIVENESS ANALYSIS

The primary effectiveness endpoint for this study is the proportion of subjects experiencing major hip injuries due to falls, as reported at the 180-day visit and will be presented for the Tango Belt and control groups using the ITT and adherence populations.

The proportion of subjects experiencing major hip injury due to falls is defined as the total number of subjects who experience a major hip injury due to a fall divided by the total number of subjects.

The primary effectiveness hypotheses are:

$$\begin{array}{l} H_0 \colon \pi_T \ \geq \ \pi_C \\ H_1 \colon \pi_T \ < \pi_C \end{array}$$

where π_T and π_C are the proportion of subjects experiencing major hip injuries due to falls in the Tango Belt and control group, respectively.

The null hypothesis (H_0) for this endpoint states that the true proportion of subjects using Tango Belt and experiencing major hip injuries due to falls is greater than or equal to the true proportion of subjects in the control group who experience major hip injuries due to falls. The alternative hypothesis (H_1) states that the true proportion of subjects using Tango Belt and experiencing major hip injuries due to falls is less than the true proportion of subjects in the control group who experience major hip injuries due to falls.

The proportion of major hip injuries by treatment group will be presented along with a 95% confidence interval using the Clopper-Pearson method. H_0 will be tested at a one-sided 0.025 level of significance using a logistic regression analysis to compare treatment groups while controlling for propensity score.

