2.2 Scientific Rationale

As a solution to the need for fall injury mitigation, Active Protective Technologies, Inc. ("APT") has developed the Tango® Belt, a wearable device primarily designed to protect geriatric individuals against major hip injuries due to a serious hip-impacting fall. Hip injuries are considered major if they are life-threatening, result in hospitalization or

emergency care, require medical intervention, or result in disability or permanent damage. A fall that results in major hip injury is described herein as a serious hipimpacting fall. The Tango Belt uses motion sensors and proprietary algorithms to determine if the wearer is experiencing a serious hip-impacting fall in progress and automatically deploys an automotive-grade cold-gas airbag around the hips to attenuate ground impact forces on the body. A longitudinal observational study by Yang et. al. analyzed recordings from thousands of real-world falls captured on closed-circuit video monitoring within the nursing home setting and determined that the vast majority of major hip injuries resulted from falls from standing height and ground-force impact to the lateral or posterolateral aspect of the hip. xiv Lastly, as referenced above, a randomized clinical trial of over 1200 subjects within nursing homes demonstrated that passive hip pads were able to reduce the incidence of hip fracture by over 80% when worn during the fall. These studies provide an evidence-based approach to mitigating fall-related major hip injuries via attenuation of ground impact forces and utilizing a belt-based form factor specifically designed to overcome common barriers to wear compliance.

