- Metrics of changes in fall mitigation plan, mobility level and fall events including falls, falls with major injury, adverse events (whether or not pertaining to the Tango Belt), emergency department visits, and hospital admissions will be taken by the site investigator or designee research assistant directly from the MDS and/or EMR within the electronic documentation system utilized at the clinical study site.
- Metrics of Tango belt wear days and wear hours/day will be provided to the site investigator or designee by sponsor or obtained from the Tango Belt Companion App.
- Metrics of device deficiencies, device discrimination between types of falls, airbag deployments, and alerting will be provided to the site Investigator or designee research assistant by sponsor from the Tango Belt cloud

Major Hip Injury Adjudication: for 90-day and 180-day adverse event reporting of Fall with Major Injury:

In the event of an identified Fall with Major Injury, the determination of Fall with Major
Hip Injury will be independently assessed by a qualified medical expert in the field of
geriatric medicine after receiving blinded data regarding the injury.

8. Assessment of Safety

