3.2 STUDY ENDPOINTS

3.2.1 PRIMARY ENDPOINT

The study's **primary effectiveness endpoint** is the proportion of major hip injuries due to fall in the subjects receiving SOC as compared to subjects receiving SOC plus the Tango Belt, as reported between enrollment and the 180-day visit.

There is no primary safety endpoint for this study. Safety of the device will be determined by analysis of adverse events as an ancillary endpoint.

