8.1 ALL ADVERSE EVENTS

The occurrence of all adverse event (AEs) will be documented for all subjects from the time of enrollment. Adverse Events will be categorized into three groups based on frequency: Single episode, Intermittent, or Continuous. This categorization is in lieu of other formal coding strategies (i.e., MedDRA). The final categorization of all AE's will be performed by the Sponsor but general definitions are as follows:

- Single Episode: Any AE's that occurred only once (Fall, death, etc.) as well as the first occurrence of an AE that occurs more than once.
- Intermittent: Subsequent AE's beyond the first of each type. If a subject had more than one of
 the same AE (i.e., fall), all occurrences of that AE after the first one will be included in the
 Intermittent category.

• Continuous: Any AE's that are ongoing and not resolved. Also, any AE that the subject lives with daily but doesn't result in death.

Summaries of incidence rates of individual AEs by frequency will be prepared. Because a subject may experience more than one AE per frequency, summaries will provide both the number of subjects experiencing at least one event and the number of events. Percentages provided will be the percent of subjects experiencing one or more adverse events. In addition, incidence of AEs will be presented by severity (mild, moderate, severe) and relationship to study device.

Subjects experiencing an event within a given frequency more than once will be counted under the maximum severity/relationship experienced.

A listing of all adverse events will include the subject number, date of onset, date of resolution, severity, AE type, the severity of AE, frequency of the event, the action taken, relationship to device, seriousness, and the outcome.

An additional listing will be provided that includes both site reported and adjudicated information for AEs that are adjudicated.

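### Blinded adjudication sees only falls already identified as major, so it can remove primary-endpoint events but never add them, and the SAP does not name the adjudicated status as the analysed variable

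*Combined protocol and SAP*

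**What the plan says.** **Definition.** Protocol 2.2 sets a broad standard. The sentence that opens "Hip injuries are considered major if they are life-threatening, result in hospitalization or" goes on to list ED treatment, a need for intervention by medical staff, and lasting damage or disability.

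**Adjudication.** The adjudication paragraph of Protocol 7.3 sets its condition in its opening words: "In the event of an identified Fall with Major Injury, the determination of Fall with Major". It then names an independent assessor, an expert in "geriatric medicine after receiving blinded data regarding the injury". Protocol 8.3 iii repeats the condition. The site starts a Fall report for every fall, but only Falls with Major Injury go to the adjudicator. No text sends any other fall there, even as a sample.

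**Source of the label.** Under Protocol 7.3 the site investigator or a designee takes falls, falls with major injury, ED visits and hospital admissions from the MDS or EMR. In the belt group the same section has the belt order entered in the chart and the care team told of the patient's participation.

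**Analysis.** SAP 3.2.1 counts injuries "as reported between enrollment and the 180-day visit", and SAP 7.2 counts them "the proportion of subjects experiencing major hip injuries due to falls, as reported at the 180-day visit". The SAP 7.2 proportion is "the total number of subjects who experience a major hip injury due to a fall divided by the total number of subjects", with no source given for the status. Adjudicated data appear once in the SAP, in section 8.1: "An additional listing will be provided that includes both site reported and adjudicated information for AEs that are adjudicated". SAP 9, which lists changes from the protocol, does not mention adjudication.

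**The concern.** Blinded expert review is the only step in classifying primary-endpoint events that is described as blinded, in a study that compares prospective belt wearers with retrospective controls. It comes after a label that is not described as blinded, so it can correct errors in one direction only. A fall wrongly labelled major can be struck out, but one wrongly left unlabelled cannot be recovered.

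The conditions of labelling also differ between groups. Belt-group labels are set prospectively by sites that know the treatment, while control labels come from records made before the belt was introduced. A difference in labelling would enter the tested contrast directly, and propensity matching on age, mobility, sex and fall history cannot remove it.

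The SAP adds a smaller difficulty. Its own listing shows that a site version and an adjudicated version of an event will both exist, yet no rule says which one is tested when they differ.

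**Working it through.** **1. What can enter the numerator.** Take a belt wearer who falls, is treated in the ED for a hip injury, and whose fall is not labelled a Fall with Major Injury.

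- Protocol 2.2: emergency care makes the injury major.
- Protocol 7.3 and 8.3 iii: without the label, the fall is not sent to the expert.
- SAP 7.2: if the adjudicated status is analysed, the event is absent because it was never adjudicated. If the site status is analysed, it is absent because it was never labelled.

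The event is lost under either reading of the SAP. The finding therefore does not depend on which status is analysed.

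**2. The plan's own figure.** SAP 4 gives 94 belt subjects at the interim analysis. Inputs from SAP 4 and 4.1: control risk 15%, 80% protective effect (belt risk 3%), 1:2 allocation, 80% power, one-sided 0.025 overall, Pocock spending. Assuming half the information at the interim, the spend is 0.025 × ln(1 + (e − 1) × 0.5) = 0.0155, so z = 2.157.

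- Pooled risk: (0.03 + 2 × 0.15)/3 = 0.11.
- n = [2.157 × √(1.5 × 0.11 × 0.89) + 0.842 × √(0.03 × 0.97 + 0.15 × 0.85/2)]² / 0.12² = (0.8266 + 0.2565)² / 0.0144 = 81.5.
- Continuity correction: (81.5/4) × [1 + √(1 + 6/(81.5 × 2 × 0.12))]² = 93.5, which rounds up to 94.

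This matches, but only if 15% is the six-month risk. SAP 4.1 calls it an annual rate with six months of follow-up. Half of it, 7.5%, gives 198 by the same formula. Both risks are therefore carried below.

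**3. Events at stake.** At 94/188 with an 80% effect: 188 × 0.15 = 28 control events and 94 × 0.03 = 3 belt events. At 188/376 with a 60% effect: 376 × 0.15 = 56 and 188 × 0.06 = 11. A few belt labels matter.

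**4. Illustration of size.** These assumptions are not in the documents: the belt has no effect, the true risk p is the same in both groups, and a share u of true events goes unlabelled in the belt group only. The observed belt risk is then p(1 − u). The test is an unadjusted one-sided pooled z test, with rejection probability found by exact binomial enumeration.

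| u | 188/376, p = 15%, level 0.025 | 188/376, p = 7.5%, level 0.025 | 94/188, p = 15%, level 0.0155 |
|---|---|---|---|
| 0 | 2.3% | 2.2% | 1.4% |
| 10% | 6.5% | 4.4% | 3.0% |
| 20% | 15.3% | 8.4% | 6.1% |
| 30% | 30.8% | 15.3% | 11.8% |

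Normal-approximation check at p = 15%, u = 20%:

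- Risks 0.12 and 0.15, pooled 0.14.
- Null SE = √(0.14 × 0.86 × (1/188 + 1/376)) = 0.0310.
- Alternative SE = √(0.12 × 0.88/188 + 0.15 × 0.85/376) = 0.0300.
- Φ[(0.03 − 1.96 × 0.0310)/0.0300] = 15.3%.

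If the same share is missed in both groups, the observed risks stay equal under no effect. There is then no bias, only fewer events and less power. If capture is better in belt wearers, the observed belt risk exceeds the control risk and the comparison is biased against the belt.

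**The case against.** A reader might infer that unblinded site labels decide the primary endpoint. The documents do not support that. Protocol 7.3 gives the determination to the blinded expert, the SAP was prepared from that protocol version, and SAP 9 lists no departure. The phrase about reporting works mainly as a time window: SAP 3.2.1 ties it to enrollment and the 180-day visit, and the SAP's version 2.0 revision removed the 90-day timepoint. This objection stands. The missing name for the analysed variable is mostly missing detail.

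It can also be said that safeguards exist. Every fall gets a Fall report, 100% of subjects have source verification of the primary endpoint (Protocol 11), and an independent observer reviews ongoing assessments (Protocol 10.4). The criteria in Protocol 2.2 are largely facts of record, and hip fractures, ED visits and hospitalizations are tested separately, so gross under-labelling might show. These steps lower the likely miss rate. None is stated to be blinded or to send an unlabelled fall to the expert, so the one-way rule remains.

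The strongest objection concerns size. Nothing in the documents points to belt-only misses of 10% to 30%. The direction could be reversed, because belt wearers have automated fall alerts and prospective Fall reports while controls come from retrospective record review. The calculation also uses a single unadjusted test, not the planned propensity-adjusted logistic regression with Pocock spending. All of this stands, so the figures are illustrative only.

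Finally, Protocol version 2.0 deliberately simplified adjudication. That is a reason to keep one adjudicator, which the fix does.

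**Conclusion.** The concern holds as a structural weakness. Identification that is not described as blinded decides which falls the blinded expert sees, so adjudication can remove primary-endpoint events but cannot add any. That follows from Protocol 7.3 and 8.3 iii read against the definition in 2.2, and it is true whichever status the SAP analyses. That belt-group sites know the treatment follows from the design rather than from an explicit statement. The lack of a named analysis variable in SAP 3.2.1 and 7.2 is a lesser drafting gap. It does not show that site labels are analysed in place of the expert's determination.

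No bias has been shown, and its direction is not known. The error rates of 6.5% to 31% (15% six-month risk) or 4% to 15% (7.5%) at 188/376 apply only if 10% to 30% of true events are missed in the belt group alone and the belt has no effect. The change is worth making because it is cheap and aligns the trigger with the protocol's own definition.

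**What to change.** 1. **Protocol 7.3 and 8.3 iii:** make the adjudication trigger a fact of record, applied alike to belt and control subjects: any fall with a recorded hip injury, or with a fall-related ED visit or hospitalization. The last two are already collected for the secondary endpoints.
2. **SAP 3.2.1 and 7.2:** state that the primary endpoint is the blinded adjudicated status and that it prevails over the site's where they differ.
3. **SAP 7.2:** add the same analysis on site-reported status as a sensitivity analysis.

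**Cost.** The sample sizes do not change. The adjudicator reads more cases, including falls already recorded: the SAP reports that roughly half the belt subjects had exited and roughly 70% of controls were enrolled when its assumptions were revised. The trigger needs a protocol amendment submitted to the IRBs; items 2 and 3 need only SAP wording. All of it should be settled before database lock.

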4.1 INTERIM ANALYSES

The study will incorporate a group sequential design (GSD) in which an interim analysis will be performed to detect an 80% protective effect of the Tango Belt at 80% power. If a significant difference is found between the prospective Tango Belt subjects and historical controls at the interim analysis, the study will be stopped, and the Tango Belt deemed superior to SOC alone. If not, sample size reestimation will be completed, and enrollment will continue until a final sample size is reached to detect a 60% protective effect of the Tango Belt at 80% power and a 5% total level of significance.

Following the steps from section 4, we assumed subjects were followed for an average of 6 months, an annual fall-with-major-hip-injury rate of 15%, and sufficient historical control subjects to allow 1:2 allocation of subjects to treatment and control. This would require 134 subjects in the prospective Tango Belt group and 268 subjects in the historical control group at the interim analysis using the Pocock alpha-spending function as well as accounting for 30% attrition. At the end of the study (should the higher effectiveness target not be achieved at interim analysis), 268 total subjects would be required in the prospective Tango Belt group and 536 subjects would be in the historical control group.

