6 GENERAL ISSUES FOR STATISTICAL ANALYSIS

Descriptive statistics for continuous variables will be summarized using descriptive statistics (number of subjects, mean, median, quartiles, standard deviation [SD], minimum, and maximum). Categorical variables will be summarized using frequencies and percentages of subjects in each category. All results will be presented by treatment and appropriate subject populations.

Statistical results such as confidence intervals and descriptive statistics for intervention primary effectiveness outcomes will be presented by site and in aggregate. Likewise, incidence of adverse events will be presented by site and in aggregate.

P-values will be one-sided and considered significant at the 0.025 level, or two-sided and considered significant at the 0.05 level of significance.

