6.5 MULTIPLE COMPARISONS AND MULTIPLICITY

There is one primary effectiveness endpoint, and it will be compared between treatment groups at a one-sided 0.025 level of significance, adjusting for propensity score (PS). There are three secondary endpoints that will also be tested using propensity score adjusted test of proportions, and the type I error rate will be adjusted for multiple testing.

To control type I error, the three secondary endpoints will be tested in a hierarchical, gatekeeping manner in the order specified below, each at a one-sided 0.025 level of significance, and only after the primary study effectiveness endpoint has been achieved in favor of the test treatment. Further, each secondary endpoint numbered 2 through 3 below will be tested for significance between treatments only if the previous secondary endpoint in the list has been shown to be significantly beneficial for the test treatment.

This hierarchical closed test procedure is used to account for multiple testing with the goal of controlling the "maximum overall Type I error rate", which is the maximum probability that has been prespecified that one or more null hypotheses are rejected incorrectly, at a one-sided 0.025 level of significance.

- 1. The proportion of Hip fractures due to fall in the subjects receiving SOC as compared to subjects receiving SOC plus the Tango Belt.
- 2. The proportion of ED visits due to fall in the subjects receiving SOC as compared to subjects receiving SOC plus the Tango Belt.
- 3. The proportion of Hospitalizations due to fall in the subjects receiving SOC as compared to subjects receiving SOC plus the Tango Belt.

There will be no adjustment for multiple comparisons across any remaining effectiveness endpoints, nor will there be adjustment for multiple comparisons across ancillary endpoints.

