7 EFFECTIVENESS ANALYSES

Given that subjects in the two comparison groups (Tango Belt vs. SOC) are not randomized and thus may not have balanced baseline characteristics, Propensity Score (PS) matching will be carried out to adjust for measured baseline confounders prior to any statistical test(s) comparing treatments on effectiveness endpoints at the interim and final analysis.

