The proportion of secondary events (i.e., hip fractures, ED visits & hospitalizations) by treatment group will be presented separately along with a 95% confidence interval using the Clopper-Pearson method. H_0 will be tested at a one-sided 0.025 level of significance using a logistic regression analysis to compare treatment groups while controlling for propensity score.

8 Adverse Events

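### The SAP's testing sections give a flat one-sided 0.025 with no look named, which conflicts with the two-look Pocock design and 5% total level in SAP 4.1

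*Combined protocol and SAP*

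**What the plan says.** **Design.** SAP 4.1 describes a group sequential design with one interim look: "If a significant difference is found between the prospective Tango Belt subjects and historical controls at the interim analysis, the study will be stopped". If the trial continues, the final size is set for a 60% protective effect at 80% power and a total significance level of 5%. The same section names the Pocock alpha-spending function, in the sentence on sample size. Protocol 10.1 names it too, for simulating size and power. SAP 4 lists alpha as one-sided 0.025.

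**Timing of tests.** SAP 7 has propensity matching done "prior to any statistical test(s) comparing treatments on effectiveness endpoints at the interim and final analysis", so effectiveness is tested at both looks.

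**Testing thresholds.**
- SAP 6, general rule: "P-values will be one-sided and considered significant at the 0.025 level" (or two-sided at 0.05).
- SAP 6.5, primary endpoint: "it will be compared between treatment groups at a one-sided 0.025 level of significance".
- SAP 6.5, secondary endpoints: "each at a one-sided 0.025 level of significance, and only after the primary study effectiveness endpoint has been achieved".
- SAP 7.2, primary: "will be tested at a one-sided 0.025 level of significance using a logistic regression analysis".
- SAP 7.3, secondaries: "will be tested at a one-sided 0.025 level of significance using a logistic regression analysis to compare treatment groups while controlling for propensity score".

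None of these four sections names a look, refers to Pocock or points back to 4.1. SAP 4.2 mentions a stopping criterion without giving its level. Neither document prints a nominal level or critical value for either look.

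**The concern.** SAP 4.1 stops the trial on a significant difference, and SAP 6 says a p-value is significant at one-sided 0.025. An analyst who takes the second to define the first would judge the interim at 0.025, and would judge the final look at 0.025 as well under 7.2. That is two chances at the full level, which is incompatible with a 5% total.

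The primary success rule is at stake. At information fraction 0.50, an interim p between 0.0155 and 0.025, or a final p between 0.0139 and 0.025, succeeds under the testing sections and fails under the Pocock boundary. In a pivotal study with non-randomised controls, that should not be settled after the data are seen. The same gap reaches the gatekept secondaries, which carry a flat 0.025 whichever look opens the gate.

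**Working it through.** **Inputs**
- Overall one-sided level 0.025 (SAP 4), matching the 5% total (SAP 4.1).
- Belt-arm sizes before attrition: 94 at the interim and 188 at the final look; controls 188 and 376 (SAP 2).
- Attrition 30% (SAP 4).
- Control event proportion 15% (SAP 4). SAP 4.1 calls 15% an annual rate, so half of it, 7.5% over six months, is run as well.

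**The plan's own figures.** 94/0.70 = 134.3 and 188/0.70 = 268.6, against a stated 134 and 268. The information fraction is 94/188 = 134/268 = 0.50. There is no stated per-look level to reproduce.

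**Boundary implied by SAP 4.1.** The Pocock-type spending function at fraction t is 0.025 × ln(1 + (e − 1)t).
- Interim, t = 0.50: 0.025 × ln(1.8591) = 0.0155, so z = 2.157.
- Left for the final look: 0.025 − 0.0155 = 0.0095. Solving P(Z1 < 2.157, Z2 ≥ c) = 0.0095 with correlation √0.50 gives c = 2.201, a nominal level of 0.0139.

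**Flat 0.025 at both looks, normal theory.** With the same correlation, P(Z1 < 1.96, Z2 < 1.96) = 0.9584. The overall one-sided error is 1 − 0.9584 = 0.0416. At information fractions 0.40 and 0.60 it is 0.0432 and 0.0398.

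**Flat 0.025 at both looks, simulation.** Binomial outcomes with no true effect, 94/188 then 188/376, unadjusted; a zero cell counts as non-significant for Wald.

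| Event proportion | Rule | Wald | Score |
|---|---|---|---|
| 15% | flat 0.025 | 0.036 | 0.039 |
| 15% | 0.0155 then 0.0139 | 0.020 | 0.022 |
| 7.5% | flat 0.025 | 0.028 | 0.035 |
| 7.5% | 0.0155 then 0.0139 | 0.013 | 0.020 |

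Wald is the closer analogue. SAP 6.3.1 imputes the primary endpoint when more than 20% is missing (30% attrition is expected) and pools with PROC MIANALYZE, which combines estimates and standard errors. The simulation does not model matching, rematching or imputation.

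**First secondary.** Multivariate normal, no true effect on the secondary, primary stopped at 2.157 or 2.201, and the error maximised over the size of the primary effect. The documents give no correlation between endpoints, so 0.5, 0.7 and 0.9 are assumed.
- Secondary at flat 1.96 at the stopping look: 0.027, 0.030 and 0.034.
- Secondary at the level of that look: 0.017, 0.018 and 0.020.

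**The case against.** The strongest reply is that the boundary is already fixed. SAP 4.1 holds the stopping rule, the 5% total and the spending function together, and the planned looks are at 94 and 188. Those facts determine 0.0155 and then 0.0139. Two looks at 0.025 would contradict the 5% total, so 0.025 in the testing sections must be the overall level. SAP 6.5 also aims to cap the chance that "one or more null hypotheses are rejected incorrectly, at a one-sided 0.025 level of significance".

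Much of this stands. A reader might infer from SAP 7.2 that the plan has no interim boundary, or that the sponsor intends to test twice at 0.025. The documents support neither: the planned boundary can be derived from 4.1, and the overall reading is the more natural one.

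The conflict between sections remains. The cap in 6.5 is a statement about the endpoint hierarchy, not about repeated looks. SAP 6 defines significance for a p-value, and the stopping rule in 4.1 relies on that word. The overall reading also leaves open which level the secondaries take if the trial stops early, since 6.5 and 7.3 give each of them 0.025.

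It is also fair that the simulations are not of the planned analysis. They show direction and rough size only.

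**Conclusion.** The point holds as an internal conflict: SAP 6, 6.5, 7.2 and 7.3, applied as written at both looks, break the 5% total that SAP 4.1 and protocol 10.1 set. It should be fixed before the interim analysis.

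The size depends on that literal reading. The overall one-sided error would be 0.042 by normal theory. In unadjusted simulation it would be 0.036 (Wald) or 0.039 (score) at a 15% event proportion, and 0.028 or 0.035 at 7.5%. For the first secondary, the maximum error is 0.027 to 0.034 over the assumed correlations. If the Pocock levels are used at both looks, as was probably meant, the primary error stays below 0.025 in every Wald and score case run. These figures therefore measure the consequence of the wording; they do not predict the trial's actual error rate.

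**What to change.** 1. In SAP 6, 6.5, 7.2 and 7.3, state that one-sided 0.025 is the overall level across both looks, and refer to the Pocock spending boundary in 4.1.
2. In SAP 4.1, print the planned one-sided levels at information fraction 0.50 (94/188): 0.0155 (z = 2.157) at the interim and 0.0139 (z = 2.201) at the final look. State that the final level is recomputed from the alpha already spent and the information actually reached.
3. In SAP 6.5 and 7.3, test the gatekept secondaries at the level of the look where the primary succeeds. This is valid and somewhat conservative.

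The cost is SAP wording, one boundary calculation per look and a somewhat stricter threshold. For a 60% effect (6% against 15%, taking 15% as the in-study proportion), simulated two-look power is 0.86 (Wald) or 0.87 (score) with the Pocock levels, against 0.92 with flat 0.025. Both are above the planned 80%. Power would be lower under either rule if 15% is an annual rate.

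This wording does not settle type I error protection for the size re-estimation that uses belt-arm outcomes (SAP 4.1.1) or for rematching at the final look (SAP 7.1). Those need their own treatment.
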